**Table 7-11 Biomarker sample collection plan in the Phase II**

Type of analysis	Visit	Mandatory /Optional	Local/ Central analysis	Methods	Material	Volume
Activ. EGFR Mut. L858R or Ex19Del	Pre-screening	Mandatory	Local	Any methods	Biopsy collected at any time	N/A
MET	Pre-screening	Mandatory	Central (Group 5: If local results available, retrospective central MET confirmation is required; if local results not available, central MET testing is required)	FISH and/or IHC Group 5: Local molecular test for MET amplification of GCN $\geq$ 5 (IHC not permitted)	- Group 1: biopsy collected at or any time after progression on last EGFR TKI line. - Groups 2 and 3: biopsy collected at any time. - Group 4: biopsy collected at any time (if treatment-naïve) or at/or any time after progression on last antineoplastic treatment (if 2/3L participants); if biopsy is not available after last treatment, the most recent available archival biopsy should be provided. Either newly obtained formalin-fixed biopsy (preferred) or archival tumor block or slides of a formalin fixed paraffin embedded (FFPE) Group 5: Biopsy collected at or any time after progression on prior line of EGFR TKI	Block or 5 slides
EGFR T790M	Pre-screening	Mandatory	Central (local results acceptable in Group 5)	PCR	- Group 1: biopsy collected at or any time after progression on last EGFR TKI line. - Groups 2 and 3: biopsy collected at any time. - Group 4: biopsy collected at any time (if treatment-naïve) or at/or any time after progression on last antineoplastic treatment (if 2/3L participants); if biopsy is not available after last treatment, the most recent available archival biopsy should be provided. Preferably same specimen than for MET. Group 5: At or any time after progression on prior line of EGFR TKI (if local result available, submit at screening or C1D1)	6 slides (unless block submitted for pre-screening)
Retrospective MET	Screening or C1D1 (pre-dose)	Mandatory	Central (Group 5 only: if local results available)	FISH or other methods	For Group 5 only: IF LOCAL RESULTS AVAILABLE. Biopsy collected at or any time after progression on first or second generation EGFR TKI.	Block or 5 slides

Type of analysis	Visit	Mandatory /Optional	Local/ Central analysis	Methods	Material	Volume

Type of analysis	Visit	Mandatory /Optional	Local/ Central analysis	Methods	Material	Volume
cell free DNA	Screening or C1D1 (pre-dose) C3D1 and every third cycle EOT	Mandatory	Central	PCR, NGS and/or other methods	Blood sample Not applicable for Group 5	2 x 10 mL
N/A: not applicable						

## **8 Safety monitoring, reporting and committees**

### **8.1 Adverse events**

#### **8.1.1 Definitions and reporting**

An adverse event is any untoward medical occurrence (e.g., any unfavorable and unintended sign [including abnormal laboratory findings], symptom or disease) in a clinical investigation participant after providing written informed consent for participation in the study. Therefore, an AE may or may not be temporally or causally associated with the use of a medicinal (investigational) product.

The investigator has the responsibility for managing the safety of individual participant and identifying adverse events.

Novartis qualified medical personnel will be readily available to advise on trial related medical questions or problems.

For participants whose EGFR and/or MET statuses are unknown and who sign the molecular pre-screening ICF, AEs which occur after signature of this consent will only be captured if they meet the definition of serious as outlined in [Section 8.2](#) and are reported to be causally related with study procedures (e.g. an invasive procedure such as biopsy). Once the main study ICF is signed, all AEs per the descriptions below will be captured in the Adverse Event CRF.

Participants whose EGFR mutation and MET statuses are known will sign the main study ICF.

Abnormal laboratory values or test results occurring after informed consent constitute adverse events only if they induce clinical signs or symptoms, are considered clinically significant, require therapy (e.g., hematologic abnormality that requires transfusion or hematological stem cell support), or require changes in study medication(s).

Adverse events that begin or worsen after informed consent should be recorded in the Adverse Events CRF. Conditions that were already present at the time of informed consent should be recorded in the Medical History page of the participant's CRF. Adverse event monitoring should be continued for at least 30 days (or 5 half-lives, whichever is longer) following the last dose of study treatment. Adverse events (including lab abnormalities that constitute AEs) should be described using a diagnosis whenever possible, rather than individual underlying signs and symptoms. When a clear diagnosis cannot be identified, each sign or symptom should be reported as a separate Adverse Event.

Adverse events will be assessed according to the Common Terminology Criteria for Adverse Events (CTCAE) version 5.0.

If CTCAE grading does not exist for an adverse event, the severity of mild, moderate, severe, and life-threatening, corresponding to Grades 1 - 4, will be used. CTCAE Grade 5 (death) will not be used in this study (but is collected as a seriousness criterion); rather, information about deaths will be collected through a Death form.

The occurrence of adverse events must be sought by non-directive questioning of the participant at each visit during the study. Adverse events also may be detected when they are volunteered

by the participant (participant) during the screening process or between visits, or through physical examination, laboratory test, or other assessments. As far as possible, each adverse event must be recorded under the signs, symptoms, or diagnosis associated with them, accompanied by the following information:

- a. The severity grade (CTCAE Grade 1-4)
- b. Its duration (Start and end dates) and the outcome must be reported
- c. Its relationship to the study treatment and other investigational treatment. If the event is due to lack of efficacy or progression of underlying illness (i.e., progression of the study indication) the assessment of causality will usually be 'Not suspected.' The rationale for this guidance is that the symptoms of a lack of efficacy or progression of underlying illness are not caused by the trial drug, they happen in spite of its administration and/or both lack of efficacy and progression of underlying disease can only be evaluated meaningfully by an analysis of cohorts, not on a single participant.
- d. Action taken with respect to study or investigational treatment (dose not changed, dose Reduced/increased, drug interrupted/permanently discontinued)
- e. Whether medication or therapy was given (no concomitant medication/non-drug therapy, concomitant medication/non-drug therapy)
- f. Outcome (not recovered/not resolved, recovered/resolved, recovering/resolving, recovered/resolved with sequelae, fatal, unknown)
- g. Whether it is serious, where a serious adverse event (SAE) is defined as in [Section 8.2.1](#) and which seriousness criteria have been met.

All adverse events should be treated appropriately. If a concomitant medication or non-drug therapy is given, this action should be recorded on the Adverse Event CRF.

Once an adverse event is detected, it must be followed until its resolution or until it is judged to be permanent (e.g. continuing at the end of the study), and assessment must be made at each visit (or more frequently, if necessary) of any changes in severity, the suspected relationship to the study treatment, the interventions required to treat it, and the outcome.

Progression of malignancy (including fatal outcomes), if documented by use of appropriate method (for example, as per RECIST criteria for solid tumors), should not be reported as a serious adverse event except if the investigator considers that progression of malignancy is related to study treatment.

Adverse events separate from the progression of malignancy (example, deep vein thrombosis at the time of progression or hemoptysis concurrent with finding of disease progression) will be reported as per usual guidelines used for such events with proper attribution regarding relatedness to the drug.

Information about adverse drug reactions for the investigational drug can be found in the Investigator's Brochure (IB).

## 8.1.2 Laboratory test abnormalities

### 8.1.2.1 Definitions and reporting

Laboratory abnormalities that constitute an Adverse event in their own right (are considered clinically significant, induce clinical signs or symptoms, require concomitant therapy or require changes in study treatment), should be recorded on the Adverse Events CRF. Whenever possible, a diagnosis, rather than a symptom should be provided (e.g. anemia instead of low hemoglobin). Laboratory abnormalities that meet the criteria for Adverse Events should be followed until they have returned to normal or an adequate explanation of the abnormality is found. When an abnormal laboratory or test result corresponds to a sign/symptom of an already reported adverse event, it is not necessary to separately record the lab/test result as an additional event.

Laboratory abnormalities, that do not meet the definition of an adverse event, should not be reported as adverse events. A Grade 3 or 4 event (severe) as per CTCAE does not automatically indicate a SAE unless it meets the definition of serious as defined below and/or as per investigator's discretion. A dose hold or medication for the lab abnormality may be required by the protocol in which case the lab abnormality would still, by definition, be an adverse event and must be reported as such.

### 8.1.3 Adverse events of special interest

Adverse events of special interest (AESI) are defined as events (serious or non-serious) which are ones of scientific and medical concern specific to the sponsor's product or program.

Adverse events of special interest are defined on the basis of an ongoing review of the safety data. AESIs are discussed in detail in the [\[capmatinib Investigator's Brochure\]](#) and [\[nazartinib Investigator's Brochure\]](#).

## 8.2 Serious adverse events

### 8.2.1 Definitions

Serious adverse event (SAE) is defined as one of the following:

- Is fatal or life-threatening
- Results in persistent or significant disability/incapacity
- Constitutes a congenital anomaly/birth defect
- Is medically significant, i.e., defined as an event that jeopardizes the participant or may require medical or surgical intervention to prevent one of the outcomes listed above
- Requires inpatient hospitalization or prolongation of existing hospitalization,

Note that hospitalizations for the following reasons should not be reported as serious adverse events:

- Routine treatment or monitoring of the studied indication, not associated with any deterioration in condition
- Elective or pre-planned treatment for a pre-existing condition that is unrelated to the indication under study and has not worsened since signing the informed consent

- Social reasons and respite care in the absence of any deterioration in the participant's general condition

Note that treatment on an emergency outpatient basis that does not result in hospital admission and involves an event not fulfilling any of the definitions of a SAE given above is not a serious adverse event

### 8.2.2 SAE Reporting

For participants with unknown EGFR and/or MET statuses and who sign the molecular pre-screening ICF, SAE collection will start upon signing the molecular pre-screening ICF. SAEs will only be reported if the event is suspected to be causally related to a study procedure as assessed by the investigator (e.g. an invasive procedure such as biopsy). SAEs will be followed until resolution or until clinically relevant improvement or stabilization. If the main ICF is not signed (molecular screen failure), SAE collection ends 30 days after the last study related procedure.

Serious adverse events considered by the investigator to be possibly related to a biopsy procedure will be indicated as such in the AE eCRF. This information will be followed-up for 30 days after the biopsy procedure.

For participants with known EGFR and/or MET statuses who sign the main study ICF, SAE collection starts at time of main study informed consent whether the participant is a screen failure or not.

To ensure participant safety, every SAE, regardless of causality, occurring after the participant has provided informed consent and until 30 days after the participant has stopped study treatment must be reported to Novartis safety immediately, without undue delay, but under no circumstances later than within 24 hours of obtaining knowledge of the events (Note: if more stringent, local regulations regarding reporting timelines prevail).

Any SAEs experienced after this 30 days period (or 5 half-lives, whichever is longer) should only be reported to Novartis safety if the investigator suspects a causal relationship to the study treatment, unless otherwise specified by local law/regulations. Recurrent episodes, complications, or progression of the initial SAE must be reported as follow-up to the original episode immediately, without undue delay, but under no circumstances later than within 24 hours of the Investigator receiving the follow-up information (Note: if more stringent, local regulations regarding reporting timelines prevail). An SAE occurring at a different time interval or otherwise considered completely unrelated to a previously reported one should be reported separately as a new event.

Information about all SAEs is collected and recorded on the Serious Adverse Event Report Form; all applicable sections of the form must be completed in order to provide a clinically thorough report. The investigator must assess and record the relationship of each SAE to each specific study treatment (if there is more than one study treatment), complete the SAE Report Form in English, and submit the completed form immediately, without undue delay, but under no circumstances later than within 24 hours obtaining knowledge of the events to Novartis safety (Note: if more stringent, local regulations regarding reporting timelines prevail). Detailed instructions regarding the submission process and requirements for signatures are to be found in the investigator folder provided to each site.

Follow-up information is submitted in the same way as the original SAE Report. Each re-occurrence, complication, or progression of the original event should be reported as a follow-up to that event regardless of when it occurs. The follow-up information should describe whether the event has resolved or continues, if and how it was treated, whether the blind was broken or not, and whether the participant continued or withdrew from study participation.

If the SAE is not previously documented in the [\[capmatinib Investigator's Brochure\]](#) and [\[nazartinib Investigator's Brochure\]](#) or Package Insert (new occurrence) and is thought to be related to the Novartis study treatment, an oncology Novartis Chief Medical Office and Patient Safety (CMO & PS) department associate may urgently require further information from the investigator for Health Authority reporting. Novartis may need to issue an Investigator Notification (IN), to inform all investigators involved in any study with the same drug that this SAE has been reported.

Suspected Unexpected Serious Adverse Reactions (SUSARs) will be collected and reported to the competent authorities and relevant ethics committees in accordance with Directive 2001/20/EC or as per national regulatory requirements in participating countries.

### **8.3 Pregnancy reporting**

If a female trial participant becomes pregnant, the study treatment should be stopped, and the pregnancy consent form should be presented to the trial participant. The participant must be given adequate time to read, review and sign pregnancy consent form. This consent form is necessary to allow the investigator to collect and report information regarding the pregnancy. To ensure participant safety, each pregnancy occurring after signing the informed consent must be reported to Novartis within 24 hours of learning of its occurrence. The pregnancy should be followed up at 1, 3 (for a live birth only) and 12 (for a live birth only) months after the estimated date of delivery to determine outcome, including spontaneous or voluntary termination, details of the birth, and the presence or absence of any birth defects, congenital abnormalities, or maternal and/or newborn complications.

Pregnancy should be recorded and reported by the investigator to the Novartis Chief Medical Office and Patient Safety (CMO&PS). Pregnancy follow-up should be recorded on the same form and should include an assessment of the possible relationship to the investigational treatment and any pregnancy outcome. Any SAE experienced during pregnancy must be reported on the SAE Report Form.

If a female partner of a male trial participant who took study treatment in this study becomes pregnant, pregnancy outcomes should be collected. Consent to report information regarding these pregnancy outcomes should be obtained from the mother.

After consent is provided, the pregnancy reporting will occur up to one year after the estimated date of delivery.

### **8.4 Warnings and precautions**

No evidence available at the time of the approval of this study protocol indicated that special warnings or precautions were appropriate, other than those noted in the provided [\[capmatinib Investigator's Brochure\]](#) and [\[nazartinib Investigator's Brochure\]](#). Additional safety information collected between IB updates will be communicated in the form of Investigator

Notifications. This information will be included in the participant informed consent and should be discussed with the participant during the study as needed.

## 8.5 Data Monitoring Committee

An independent data monitoring committee will not be formed for this study.

### For the Phase Ib part of the study

Novartis will host investigator teleconferences on a regular basis during the study. Further, Novartis and the investigators will meet at the end of each treatment cohort to discuss and evaluate all of the gathered safety data. At the dose escalation teleconference the clinical course (safety information including both DLTs and all CTCAE Grade 2 or higher toxicity data during the first cycle of treatment, and PK data) for each participant in the current dose cohort will be described in detail. Updated safety data on other ongoing participants, including data in later cycles, will be discussed as well.

Dose escalation decisions will be based on a clinical synthesis of all relevant available data and not solely on DLT information. Selection of the actual dose for the next cohort of participants will be guided by the BLRM's (with EWOC) recommendation, and a medical review of relevant clinical, PK and laboratory data. Novartis and the investigator parties must reach a consensus on whether to declare MTD, escalate the dose any further, or whether to de-escalate and/or recruit an additional cohort of participants at the current dose level (see ).

### Phase II part of the study

This is a single arm trial (i.e. no comparator arm) and there is no a priori information as per the FDA Guidance of "situations in which safety concerns may be unusually high" or the participant population being studied are "potentially fragile population such as children, pregnant women or the very elderly, or other vulnerable populations, such as those who are terminally ill or of diminished mental capacity." Thus, an independent data monitoring committee will not be constituted for the Phase II part of this study.

The Novartis clinical team will review the safety data on a regular basis. A review of the safety data and assessment of futility, based on the calculated Bayesian probability of success (PoS) will be performed at the interim analysis of Group 3 (first line) by the Novartis clinical trial team and shared with the investigators in a data review meeting.

At the time of the interim analysis for Group 3, the best overall response for each participant will be derived from the overall lesion response assessments performed by the Investigator. These will be used to calculate the overall response rate for the respective group and a Bayesian analysis will be performed to estimate the PoS of the trial given the current data (see [Section 10.9](#) for details).

It is envisioned that the team may make three types of recommendations at the interim analysis, namely:

- No safety or efficacy issues, ethical to continue the study group as planned
- PoS is too small and the study group is terminated due to lack of significant activity
- Serious safety concerns precluding further treatment in the study group, regardless of efficacy.

At the time of the interim analysis for Group 5, the response for each participant will be derived from the overall lesion response assessments performed by the Investigator. These will be used to calculate the ORR and a Bayesian analysis will be performed to estimate the POS of the trial given the current data (see [Section 10.9](#) for details).

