### 10.5.1 Variable

**Phase Ib:** Incidence of dose limiting toxicities (DLTs) in Cycle 1. Estimation of the MTD of the study treatment will be based upon the estimation of the probability of DLT in Cycle 1 for

participants in the DDS. This probability is estimated by the model described in Section 10.4.2.

**Phase II, Group 1–3:** Overall response rate, determined as the proportion of participants experiencing a best overall response of confirmed CR or PR per RECIST 1.1 at any time on study by investigator assessment.

ORR will be estimated by group and for Group 1 by T790M status as assigned based on baseline mutation status and prior systemic antineoplastic therapy.

**Phase II, Group 4:** Frequencies of treatment-emergent adverse events.

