#### **Group 3 (EGFRmut, T790M negative, any MET, 1L antineoplastic)**

The ORR will be classified according to the following intervals:

- [0, 40%) unacceptable anti-tumor activity
- [40%, 55%) limited anti-tumor activity
- [55%, 70%) moderate anti-tumor activity
- [70%, 100%] strong anti-tumor activity

An observed ORR  $\geq 55\%$  based on Investigators' assessments will be considered clinically meaningful in this group.

The preliminary anti-tumor activity of the study treatment will be declared if the following two conditions are both fulfilled:

- The posterior median ORR is equal to or greater than 55%
- The posterior risk of being in the unacceptable anti-tumor activity interval is lower than 5%

This will require observing at least 22 responses in 40 participants. Otherwise, the inferential summaries for the 4 intervals above will be assessed for further characterization of the anti-tumor activity. A minimally informative beta distribution with parameters  $a = 1$  and  $b = (1 - 0.55)/0.55 = 0.818$  based on an assumed mean response rate of 0.55 will be used as prior distribution for the Bayesian estimation of the ORR.

An interim analysis for futility will be performed when approximately 20 participants have completed at least 4 cycles of treatment or discontinued treatment prior to that time. More details on the interim analysis are presented in nazartinib.

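### Section 8.5 shares the Group 3 interim futility assessment with the investigators who read the primary endpoint and does not limit what is disclosed: an avoidable risk of assessment drift, of unknown size

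*Protocol*

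**What the plan says.** For the Phase II part, Section 8.5 says of Group 3: "A review of the safety data and assessment of futility, based on the calculated Bayesian probability of success (PoS) will be performed at the interim" look. The work is done "by the Novartis clinical trial team and shared with the investigators in a data review meeting". Interim best overall response "will be derived from the overall lesion response assessments performed by the Investigator". The section then lists three possible recommendations: continue, stop for lack of activity, or stop for safety. It also states: "An independent data monitoring committee will not be formed for this study".

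Section 10.5.1 defines the primary variable for Groups 1 to 3 as the proportion with a "best overall response of confirmed CR or PR per RECIST 1.1 at any time on study by investigator assessment". The interim and final analyses therefore use the same readers.

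Section 10.5.2.2 sets two posterior conditions for declaring preliminary activity in Group 3 and translates them into a count: "This will require observing at least 22 responses in 40 participants". Section 10.9 places the futility look at about 20 participants, stops if PoS is below 0.10 (fewer than 9 of 20), and prints Table 10-2, which gives the PoS for 8 to 12 responders.

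On controls, Section 7.2.1 requires each response to be confirmed at least 4 weeks later. It has images collected and stored centrally for a possible independent review, whose results may be used for secondary analyses. The supportive analysis in Section 10.5.4 changes the analysis set, not the reader.

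**The concern.** Pooled interim efficacy is usually kept from the people whose judgement forms the endpoint. Here the assessors may receive it while part of the group is still unread. In an open-label, single-arm trial an investigator already knows the results of his or her own participants. The meeting could add the pooled result and its distance from a published target.

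Some room for judgement exists even when readers act in good faith. The RECIST appendix (Section 14.1) lets the investigator replace an unknown response with a definitive one, decide whether a reappearing lesion is new, and follow an equivocal new lesion. Section 14.1.4.4 allows discrepant readings to be queried but says that the investigator's assessment is not overruled.

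At stake is the Group 3 declaration of preliminary activity. Table 10-5 gives its probability on the premise that the assessed response rate is the same before and after the look. Knowledge of the pooled result could disturb that premise.

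**Working it through.** **Inputs.** Prior Beta(1, 0.818), success conditions and target of 22/40: Section 10.5.2.2. Look at 20, continue with 9 or more, PoS table: Section 10.9. Stated operating characteristics: Table 10-5 in Section 10.10.

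**1. The success count reproduces.** With r responders in 40 the posterior is Beta(1 + r, 0.818 + 40 − r).
- r = 22: median 0.551, P(ORR < 40%) = 0.025. Both conditions are met.
- r = 21: median 0.527, P(ORR < 40%) = 0.0504. Both conditions fail.

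So 22 is the minimum, and a single reading can decide the declaration.

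**2. Table 10-2 reproduces.** PoS is the beta-binomial probability of at least 22 − r₁ responders in the remaining 20, given Beta(1 + r₁, 0.818 + 20 − r₁).

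| r₁ of 20 | PoS computed | PoS stated | Still needed of 20 |
|---|---|---|---|
| 8 | 0.043 | 0.04 | 14 |
| 9 | 0.140 | 0.14 | 13 |
| 10 | 0.326 | 0.33 | 12 |
| 11 | 0.570 | 0.57 | 11 |
| 12 | 0.789 | 0.79 | 10 |

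Each PoS belongs to one count. If the look is at 20 participants, a reader shown 0.33 can infer 10/20 and 12 still needed.

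**3. Table 10-5 reproduces.** With true ORR p,

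P(success) = Σ over r = 9 to 20 of P(Bin(20, p) = r) × P(Bin(20, p) ≥ 22 − r).

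At p = 0.40, 0.45, 0.50 and 0.55 this gives 0.038, 0.129, 0.309 and 0.553. The stopping probability P(Bin(20, p) ≤ 8) is 0.596, 0.414, 0.252 and 0.131. All match.

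**4. Sensitivity to drift after the look.** Let f be the share of true non-responders among the last 20 who are read as responders. The documents give no value, so f is an assumption. The second-stage rate becomes q = p + f(1 − p), and q replaces p in the second factor above.

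| True ORR | f = 0 | f = 5% | f = 10% | f = 15% |
|---|---|---|---|---|
| 40%: q | 0.400 | 0.430 | 0.460 | 0.490 |
| 40%: P(success) | 0.038 | 0.056 | 0.079 | 0.107 |
| 45%: q | 0.450 | 0.478 | 0.505 | 0.532 |
| 45%: P(success) | 0.129 | 0.167 | 0.210 | 0.257 |

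At a true ORR of 40%, 12 of the last 20 are expected to be true non-responders (20 × 0.60). So f = 5% to 15% means 0.6 to 1.8 readings changed on average (12 × 0.05 to 12 × 0.15).

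**5. How many readings are exposed.** The look waits for about 20 participants to complete 4 cycles of 28 days, which is 16 weeks, or to discontinue earlier. Scans start at Cycle 3, after 8 weeks. Section 10.9 states a recruitment halt for the Group 5 look but none for Group 3, so some later participants may already have been read. For a group of 40, 20 is an upper bound, and the figures in step 4 are at that bound.

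**The case against.** The strongest objection is that the text does not say what is shown. Section 8.5 shares an assessment based on PoS, and the outcomes it lists are three categories. A reader might infer that each investigator will be told the exact count still required. The document does not state that; it only leaves it possible. This part of the objection stands, and it is why the point is conditional on the PoS or ORR being disclosed.

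A reader might also infer that readings will drift, or that Table 10-5 is wrong. Neither is supported. The tables reproduce, and no drift rate can be taken from the documents. Conditioning on a near-miss such as 10/20 would make the effect look larger, so the figures given are unconditional.

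Safeguards exist. Responses follow RECIST 1.1 and need confirmation, images are stored, and discrepancies from the programmed response can be queried. These reduce the risk and would allow a later check. They do not remove it, because no independent reading of the primary endpoint is required.

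The stakes are also limited. The aim is to estimate preliminary activity in a single-arm group, and below 22 responses the plan goes on to interval summaries.

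Finally, with no independent committee, the data review meeting is the described route by which physicians outside the sponsor see the interim conclusion. That is a fair consideration, but safety information and the continue/stop decision would still reach them at once.

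Extending the point to Group 5 might seem natural. The sharing sentence names Group 3 only, and the Group 5 paragraph in Section 8.5 has no counterpart.

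**Conclusion.** The point holds as an avoidable risk in Group 3. The plan shares a PoS-based assessment with the assessors of its primary endpoint, prints the target and the table that would turn a PoS into a count, and sets no limit on disclosure in the part of the protocol available here. Part 1 of the document is not shown.

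The size is unknown. Under the assumed 5–15% misreading of true non-responders in up to 20 later participants, the probability of success roughly rises by a factor of 1.5 to 2.8 at a true ORR of 40% (0.056/0.038 to 0.107/0.038) and 1.3 to 2.0 at 45% (0.167/0.129 to 0.257/0.129). With no drift, or if only the decision is communicated and readings do not shift, the stated operating characteristics stand. Nothing here shows an error in the design figures. This is an inexpensive improvement, not a flaw that invalidates the group.

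**What to change.** In Section 8.5, state for Group 3 that investigators receive the safety review and the continue/stop decision, and that the responder count, ORR and PoS remain with the sponsor's interim team until the Group 3 primary analysis. No change is proposed for Group 5.

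The cost is one sentence. Investigators would not see pooled interim efficacy until the primary analysis. The protection is partial: because the boundary is printed, a decision to continue still implies roughly 9/20 or more if the rule is followed. What is withheld is how far above that the result lies, and so how many further responses are needed.
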